12.3.5.2. Subjects with office-based intervention for recurrence

Adverse procedural/device event rates and QOL information will be collected for 36 months, regardless of whether or not the subject has office-based intervention for recurrence.

Event rate for each of device-related or procedure-related adverse events of specified AE type (mesh erosion, mesh exposure, dyspareunia) during the period after the intervention will be summarized by treatment group. Treatment groups will be compared using Cox regression for the event-free survival time (starting at the time of first office based intervention) with treatment arm.

For each QOL instrument, a comparison using a t-test will be performed between native tissue repair and mesh group on the basis of QOL score at the first scheduled follow-up after office-based intervention for recurrence.

A two sample t-test will be used to compare groups with office-based intervention for recurrence and without intervention within each treatment group. QOL score change will be reported from the last follow-up visit before office-based intervention for recurrence, to the next scheduled follow-up visit after office-based intervention for recurrence within each treatment group. For those subjects without recurrence, we will use baseline as the “before” time point in analysis, and the QOL data at 6 month follow-up visit as the “after” time point.

Similarly, event rate for each adverse device and procedure-related event type specified (mesh erosion, mesh exposure, dyspareunia) will be compared between subjects with office-based intervention for recurrence and those without. This will be done using a Cox regression of time to the first onset of each adverse event after the starting time to compare groups with office-based intervention for recurrence and within each treatment group. The starting time will be baseline for those subjects without intervention, and time of office-based intervention for recurrence for those with intervention.

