12.3.5.3. Subjects with surgical intervention for recurrence

The above mentioned analyses for the subgroup with office based intervention for recurrence will be repeated for subjects with surgical intervention for recurrence.

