12.3.7. Sub-Analysis for Interventions for Complications

The above sub-analyses in Section 12.3.5 will be repeated for re-surgery for complications or recurrence.

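### In the within-arm comparisons of women with and without an intervention, only the comparison group's quality-of-life change spans the index surgery, and the two Cox clocks start at different points

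*Combined protocol and SAP*

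**What the plan says.** Section 12.3.5.2 sets out two within-arm contrasts.

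- **QOL.** "A two sample t-test will be used to compare groups with office-based intervention for recurrence and without intervention within each treatment group". For intervened women, "QOL score change will be reported from the last follow-up visit before office-based intervention for recurrence, to the next scheduled follow-up visit" after it. For the others: "For those subjects without recurrence, we will use baseline as the" before point, and the month 6 visit supplies the after point. The comparison group is called without intervention in one sentence and without recurrence in the other.
- **Adverse events (mesh erosion, mesh exposure, dyspareunia).** The method is "a Cox regression of time to the first onset of each adverse event after the starting time". The clocks differ by group: "The starting time will be baseline for those subjects without intervention, and time of office-based intervention for recurrence for those with intervention".

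Section 12.3.5.3 says the analyses "will be repeated for subjects with surgical intervention for recurrence". Section 12.3.7 adds: "The above sub-analyses in Section 12.3.5 will be repeated for re-surgery for complications or recurrence".

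**The concern.** A with-versus-without contrast is read as showing what goes along with the intervention. Here the two groups are measured over different parts of the post-surgical course. One QOL change contains the index operation and the other does not. One Cox clock starts at or before surgery and the other starts months after it. Following the plan exactly would produce differences that come from the choice of windows.

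A reader could conclude that women who needed an intervention gained less QOL, or had more or fewer adverse events afterwards, when the design alone generates that result. What is at stake is the reading of these secondary sub-analyses. The primary endpoints, the sample size, and the between-arm comparisons in the same section are not touched; the between-arm Cox model starts both arms at the first intervention.

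**Working it through.** The plan gives no sample size, effect or event count for these contrasts, so there is no figure to reproduce. The check places the windows on one time axis and then illustrates the size.

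**Timing, with index surgery as month 0**

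| Item | With intervention | Comparison group | Source |
|---|---|---|---|
| QOL before point | a follow-up visit, after month 0 | baseline, before month 0 | 12.3.5.2, 11.4.2, 11.4.5 |
| QOL after point | next scheduled visit | month 6 | 12.3.5.2 |
| Index surgery inside the window? | no | yes | follows from the rows above |
| Cox start | the intervention | baseline | 12.3.5.2 |

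Section 11.4.2 puts baseline before surgery, by up to 3 months. Section 11.4.5 counts follow-up visits from discharge. Sections 10.1 and 21.1 record adverse events only once a woman is enrolled, that is, from the incision. If baseline means the visit, the comparison group has a stretch of up to 3 months in which no event can be recorded.

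**QOL**

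Let *g* be the index-surgery gain in SD units, with improvement positive and no change around the intervention. The expected difference (intervened minus comparison) is 0 − *g* = −*g*, whatever the numbers in the groups.

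For a pooled two-sided 5% t-test with 163 degrees of freedom, the noncentrality is *g* / √(1/n₁ + 1/n₂), where n₂ = 165 − n₁. The 165 per arm is from Section 8.1. The values of *g* are assumed. The count n₁ = 3 borrows the 2% office-based rate stated for complications in Section 12.3.3 (0.02 × 165 = 3.3), and n₁ = 20 is assumed.

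| n₁ / n₂ | *g* | Noncentrality | Pooled t, false significance | Welch t |
|---|---|---|---|---|
| 3 / 162 | 0.5 | 0.5 / 0.583 = 0.86 | 13.7% | about 10% |
| 3 / 162 | 1.0 | 1 / 0.583 = 1.72 | 40.0% | about 20% |
| 20 / 145 | 0.5 | 0.5 / 0.239 = 2.10 | 54.9% | about 52% |
| 20 / 145 | 1.0 | 1 / 0.239 = 4.19 | 98.6% | about 98% |

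The Welch figures are simulated (60,000 trials). The plan does not say which version of the test it means. More intervened women make the false finding more certain; the bias itself stays at −*g*.

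**Cox**

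For a woman intervened at time *t₀*, the planned model compares hazard h(*t₀* + *u*) with h(*u*) at clock time *u*. For a Weibull hazard with shape *k* the ratio is ((*t₀* + *u*)/*u*)^(*k*−1). At *t₀* = *u* = 12 months this is 1 for *k* = 1, 2^(−0.5) = 0.71 for *k* = 0.5, and 2^0.5 = 1.41 for *k* = 1.5. So no bias arises with a constant hazard and a start at surgery. Early events push the hazard ratio down, and late events push it up.

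The simulation assumed no true effect, 15% intervened uniformly over months 3 to 30, and 15% with an event by month 36:

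| Baseline relative to surgery | Constant (*k* = 1) | Early (0.7) | Early (0.5) | Late (1.5) |
|---|---|---|---|---|
| At surgery | 0.99 | 0.69 | 0.47 | 1.55 |
| 0–3 months before, uniform | 1.08 | 0.72 | 0.50 | 1.75 |
| 3 months before | 1.18 | 0.76 | 0.53 | 1.96 |

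Results are nearly the same at a 9% event rate, the dyspareunia figure in Section 12.1.2.2. With time from surgery and a time-dependent intervention, the hazard ratio is 0.97–1.02 without confounding. At 165 per arm and no lag, the planned model falsely rejects in 0.4–10.4% of trials for shapes 0.5–1.0 and 10.9–16.5% for shape 1.5. The Cox fault is therefore mainly a biased estimate.

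**The case against.** The best defence is that each group is anchored on its own treatment episode: QOL and events after a re-intervention set against QOL and events after an index repair that needed none. The index-surgery gain would then be the intended comparator. However, the section never states that purpose, and it labels the groups as with and without intervention.

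Other points carry more weight:

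- **Cox.** With a constant hazard and baseline at surgery there is no bias. Anything else needs an event pattern the documents do not give, and the 3-month row is the extreme case. This stands: the direction is unknown.
- **Sizes.** The gains, intervention counts and event patterns are assumed, and the count of 3 comes from a rate for complications, not recurrence. This stands. The QOL bias of −*g* does not depend on the counts.
- **The remedy.** With QOL change compared over the same interval and adjusted for the earlier score, a true null is rejected in 4.8–5.3% of trials if intervention depends only on the recorded score. If it also depends on unrecorded worsening, the rates are 12.7%, 28.4% and 55.0% with 3, 8 and 20 intervened. Under shared frailty the time-dependent Cox model gives 1.26–1.33. This confounding is real, and it would enter the planned contrasts too. Correcting the windows removes only the error that the plan itself introduces.
- **Importance.** These are secondary analyses without stated hypotheses, and at 1–2% intervened there would be little to test. That limits the consequence but does not make the windows comparable.

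**Conclusion.** The concern holds. The QOL half follows from the plan's definitions alone: the contrast is offset by the full index-surgery gain, whatever that gain is. The Cox half is a misalignment of time since surgery. It is harmless only if the hazard is constant and baseline coincides with surgery; otherwise it can bias the hazard ratio either way. All sizes are illustrative, because the documents give no rate of intervention for recurrence, no QOL gain and no time pattern for these events. The correction should be made before these sub-analyses are run, but it does not bear on the study's main conclusions.

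**What to change.** In Section 12.3.5.2, carried through to 12.3.5.3 and 12.3.7:

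1. **QOL.** Compare intervened and non-intervened women over the same scheduled post-operative visit interval, adjusting for the score at its start. State how intervals are matched and how a woman contributing several intervals is handled.
2. **Comparison group.** Use without intervention throughout. Without recurrence leaves no place for a woman who recurs but has no intervention, which Section 11.5 allows.
3. **Missing before scores.** Month 2 collects PFDI-20 and TOMUS but not PFIQ-7 or PISQ-12 (Section 11.4.6). For interventions before month 6 the latter two have no post-operative before score; list those women descriptively.
4. **Cox.** Measure time from index surgery for everyone and enter the intervention as a time-dependent covariate. State whether a woman whose first event of that type preceded the intervention leaves the risk set then, or re-enters at the intervention with a robust variance. Without frailty, 5–10% of intervened women were in this position in the simulations.
5. **Reporting.** Present results as descriptive associations. Where few women are intervened, give descriptive statistics only; the stated 1–2% rates for complications imply about 2–3 of 165.
6. **Leave alone** the between-arm Cox model that starts at the first intervention.

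The cost is some SAP wording and reprogramming. Apart from PFIQ-7 and PISQ-12 at month 2, the data are already collected. The corrected contrasts remain confounded by the reasons for intervening.

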12.3.5.3. Subjects with surgical intervention for recurrence

The above mentioned analyses for the subgroup with office based intervention for recurrence will be repeated for subjects with surgical intervention for recurrence.

12.3.5.4. Subjects with surgical intervention for recurrence or complications

Each of device-related or procedure-related adverse events during the period after the re-surgery will be summarized by the vaginal compartment(s) (i.e. apical only, anterior only, apical and anterior) treated in the index procedure within each treatment group.

12.3.6. **Additional Data Analyses**

- Assessment of EQ-5D score for health status at 12, 24 and 36 month as compared to baseline
- Assessment of SSQ-8 score for surgical satisfaction at 6, 12, 24 and 36 month

Propensity score adjusted confidence intervals described in Section 12.2.3 (Propensity Score Methodology) will be used to summarize EQ-5D and SSQ-8 score improvements between two groups.

12.3.7. Sub-Analysis for Interventions for Complications

The above sub-analyses in Section 12.3.5 will be repeated for re-surgery for complications or recurrence.

12.3.8. Interim Analysis

An interim analysis will be performed at 12 months from the last subject enrolled in the study; all subjects will be followed to 36 months for the primary endpoint and final analysis. This analysis will consist of the primary and some or all of the secondary endpoints and demographics if deemed necessary.

Descriptive statistics by treatment arm along with 95% confidence interval for the treatment difference will be reported after adjusting for propensity scores. The descriptive statistics includes mean, standard deviation, n, minimum, and maximum for continuous variables and frequency statistics for discrete variables¹.

12.3.8.1. Hypotheses²

The interim analysis hypothesis is that transvaginal mesh repair (treatment) is non-inferior to traditional native tissue repair (control) in both effectiveness and safety at 12 months.

Statistical testing will be performed to evaluate whether transvaginal mesh repair (treatment) is non-inferior to native tissue repair with respect to the composite treatment success endpoint. The null hypothesis is that the success rate for Uphold LITE is inferior to that of the control at a non-inferiority margin of 12%:

$$H_0: \pi_{treatment} - \pi_{control} \leq -12\%$$

where $\pi_{treatment}$ and $\pi_{control}$ is the success rate in the treatment and control group, respectively. The alternative hypothesis is:

$$H_a: \pi_{treatment} - \pi_{control} > -12\%$$

The rejection of null hypothesis indicates the non-inferiority of transvaginal mesh repair.

If non-inferiority is demonstrated, then the superiority of transvaginal mesh repair at 12 months will be evaluated, for which the hypotheses are:

¹ To support United States Premarket Approval Activities, as agreed to on the Presubmission call held on May 24, 2017 (Q170382), Boston Scientific will submit descriptive statistics for the submission of the PMA, which per reclassification document number 2015-33165, is required to be accepted and filed on or before July 5, 2018.

² To support the continued review of the Premarket Approval Application for the United States, Boston Scientific will submit hypothesis testing as an Amendment to the initial PMA following acceptance and filing.

$$H_0: \pi_{treatment} \leq \pi_{control}$$

$$H_a: \pi_{treatment} > \pi_{control}$$

The rejection of null hypothesis indicates the superiority of transvaginal mesh repair.

Statistical testing will be performed to determine if the serious complication rate (i.e. serious adverse device effects and serious procedure-related adverse events) of the treatment group is non-inferior to the control group at 12 months. The null hypothesis is that the serious complication rate in treatment group is greater than or equal to the rate in control group plus margin of 10%:

$$H_0: \pi_{treatment} - \pi_{control} \geq 10\%$$

where $\pi_{treatment}$ and $\pi_{control}$ is the serious complication rate in the treatment group and control group, respectively. The alternative hypothesis is:

$$H_a: \pi_{treatment} - \pi_{control} < 10\%$$

12.3.8.2. Statistical Methods

The comparisons of mesh repair to native tissue repair will be based on a two-sided 90% confidence interval for the treatment difference. The confidence interval will be calculated based on the pooling of treatment differences across propensity score strata for a binary endpoint, as described in Section 12.2.3 (Propensity Score Methodology).

Missing 12 month data for the composite efficacy endpoint will be handled by multiple imputation under a logistic regression model using a fully conditional specification. The imputation model will include treatment group and primary efficacy outcome at 2 and 6 month. A total of 5 imputed data sets will be generated.

The following methods will also be used as sensitivity analyses:

- Observed data only
- Tipping point analysis

12.3.9. **Justification of Pooling**

The analyses will be presented using pooled data across institutions. For each group, an analysis of the poolability will be made using logistic regression for binary outcomes, or analysis of variance for continuous outcomes, to assess differences between study institutions and to justify pooling data across institutions. Centers with less than 5 ITT patients may be combined.

12.3.10. **Multivariable Analyses**

For each treatment group, univariate and multivariate analyses will be performed to assess possible predictors of the improvement in pelvic organ prolapse at 36 month, mesh-related complications and subject reported outcomes. Possible predictors may include, but not limited to, demographic/baseline data and risk factors data. Factors from the univariate model with $p \leq 0.20$ will also be put into multivariate model using a stepwise procedure in a

logistic regression model. The significance thresholds for entry and exit into the model will be set to $p < 0.10$. Analysis of Covariance (ANCOVA) will be performed for subject reported outcome with appropriate predictors.

13. Data Management

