12.1.1.2. Sample Size

The statistical power calculation is based on a superiority assumption with a binary primary outcome. Success, based on a composite endpoint of anatomic and symptomatic success at 36 month is assumed to be 70.0% for the native tissue arm and 85.0% for transvaginal mesh arm.¹⁷⁻²¹ With 2-sided type I error of 0.05 and type II error of 0.1 (power 90%), 316 subjects (158 subjects per arm) are needed to detect 15% difference of transvaginal mesh to native tissue repair. In addition to a superiority assumption, statistical testing will be performed for non-inferiority using a margin of -12%.

To assess for safety, the overall complication rate (i.e. serious adverse device effects and serious procedure-related adverse events) is anticipated to be approximately 14%.²² With type I error of 0.05 and type II error of 0.20 (power 80%), 298 subjects (149 subjects per arm) are needed to detect non-inferiority with a margin of 10%.

To assess for office-based interventions for complications, the rate is anticipated to be approximately 2%.²² With type I error of 0.025 and type II error of 0.10 (power 90%), 330 subjects (165 subjects per arm) are needed to detect non-inferiority with a margin of 5%.

To assess for of surgical intervention for complications, the rate is anticipated to be approximately 1%.²² With type I error of 0.025 and type II error of 0.10 (power 90%), 260 subjects (130 subjects per arm) are needed to detect non-inferiority with a margin of 4%.

Non-surgical subjects will be enrolled by the PFD Registry and analyzed in this clinical study. Non-surgical subjects will not be enrolled into this clinical study. Using the above calculations and assuming a 20% loss to follow-up rate, a total of 414 subjects (207 per study arm) will be enrolled to achieve the primary endpoint of success at 36 months.

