12.1.1.3. Statistical Methods

For the primary efficacy endpoint, the comparisons of mesh repair to native tissue repair will be based on a two-sided 95% confidence interval for the treatment difference (mesh minus native tissue repair). If the entire confidence interval is above zero, superiority of mesh repair to native tissue repair will be demonstrated. The confidence interval will be calculated based on the pooling of treatment differences across propensity score strata for a binary endpoint, as described in Section 12.2.3 (Propensity Score Methodology).

If any data on the primary efficacy endpoint is missing, multiple imputation will be performed in which the missing values will be imputed five times under a logistic distribution model, using a fully conditional specification that includes the treatment arm and the assessments of the treatment success endpoint at each of 2, 6, 12, 18, and 24 months. As a sensitivity analysis, the comparison of treatments will also be performed using the following methods:

- Tipping point analysis
- Available cases only (i.e., only the subjects for whom the endpoint was assessed)

For the primary safety endpoint, the proportions will be calculated using for the numerator the number of subjects with an endpoint event and for the denominator the number of subjects in the analysis population (ITT and per protocol group). Non-inferiority will be evaluated using a two-sided 90% confidence interval for the treatment difference (mesh minus native tissue repair). If the entire confidence interval is below the margin (10%), non-inferiority will be demonstrated. The confidence interval will be calculated based on the pooling of treatment differences across propensity score strata for a binary endpoint, as described in Section 12.2.3 (Propensity Score Methodology).

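### The 12-month superiority test is judged on a two-sided 90% interval, although the plan requires 95% for superiority on the same composite at 36 months

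*Combined protocol and SAP*

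**What the plan says.** Section 12.3.8.1 plans three tests at 12 months: non-inferiority on the effectiveness composite (margin 12 points), superiority on that composite if non-inferiority is met, and non-inferiority on serious complications (margin 10 points). The second is introduced so: "If non-inferiority is demonstrated, then the superiority of transvaginal mesh repair at 12 months will be evaluated". Footnote 2 says the sponsor "will submit hypothesis testing as an Amendment to the initial PMA following acceptance and filing".

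Section 12.3.8.2 then gives one interval for all of this: "The comparisons of mesh repair to native tissue repair will be based on a two-sided 90% confidence interval for the treatment difference". It makes no exception for superiority.

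For the same composite at 36 months, Section 12.1.1.3 says that "the comparisons of mesh repair to native tissue repair will be based on a two-sided 95% confidence interval for the treatment difference", and sets the rule: "If the entire confidence interval is above zero, superiority of mesh repair to native tissue repair will be demonstrated". That section keeps a 90% interval for safety non-inferiority. Section 12.1.1.2 sizes the effectiveness comparison at the matching level: "With 2-sided type I error of 0.05 and type II error of 0.1 (power 90%), 316 subjects (158 subjects per arm) are needed".

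The opening of Section 12.3.8 also mentions a 95% interval, but attaches it to descriptive reporting: "Descriptive statistics by treatment arm along with 95% confidence interval for the treatment difference will be reported after adjusting for propensity scores".

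**The concern.** At 36 months the plan assigns interval levels by type of test: 95% for effectiveness superiority, 90% for safety non-inferiority. At 12 months that distinction disappears, and the superiority test takes the level the plan otherwise uses for safety non-inferiority. Its nominal one-sided error doubles from 2.5% to 5%, with no reason given.

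The 12-month tests go to the regulator in support of a marketing application. Superiority could be claimed there on evidence that fails the plan's own standard for superiority on this composite. The descriptive 95% interval in the same report could include zero beside that claim.

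**Working it through.** **Inputs from the plan.** Success 70% (native tissue) and 85% (mesh), two-sided 0.05, power 90%, 158 per arm, 207 enrolled per arm (Section 12.1.1.2); 165 per arm for the 36-month analysis (Section 8.1). **Assumed:** a common 12-month success rate of 70-85%, and 12-month information between 165 and 207 per arm. The calculations use the variance of Section 12.2.3 without strata unless stated.

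**1. The plan's own sample size.** With unpooled variance,

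n = (1.960 + 1.282)² × (0.70×0.30 + 0.85×0.15) / 0.15² = 157.6, so 158 per arm, as stated.

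At one-sided 0.05, 1.645 replaces 1.960 and n = 128.5, so 129. The stated number therefore rests on one-sided 2.5%. By contrast, the safety figure of 149 per arm (14% rate, 10-point margin, 80% power) reproduces at one-sided 5%; one-sided 2.5% would need 190.

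**2. The non-inferiority step.** Superiority requires a lower limit above 0. Any such limit is also above -12 points, so every superiority finding has already passed the first step. The sequence leaves the superiority error rate unchanged.

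**3. False-superiority rate.** Nominally this is 1 - Φ(1.645) = 5.0% against 1 - Φ(1.960) = 2.5%. Exact binomial enumeration of the rule that the lower limit exceeds 0, with equal true rates:

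| Common success | 165/arm, 90% | 165/arm, 95% | 207/arm, 90% | 207/arm, 95% |
|---|---|---|---|---|
| 70% | 5.13% | 2.59% | 5.02% | 2.53% |
| 75% | 5.05% | 2.61% | 5.09% | 2.55% |
| 80% | 5.06% | 2.64% | 5.13% | 2.59% |
| 85% | 5.12% | 2.59% | 5.09% | 2.59% |

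Simulating the five-stratum estimator of Section 12.2.3, with equal strata and 165 or 205 per arm, gives about 5.3-5.4% and 2.7%. The doubling remains.

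**4. Results that would change.** At 80% average success:

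- 165 per arm: SE = √(2×0.8×0.2/165) = 0.0440. Thresholds are 1.645×SE = 7.2 points and 1.960×SE = 8.6 points.
- 207 per arm: SE = √(2×0.8×0.2/207) = 0.0393. Thresholds are 6.5 and 7.7 points.

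Observed gains between the two thresholds count as superior only under the 90% interval. As success moves from 70% to 85%, the band moves from 8.3-9.9 to 6.5-7.7 points (165 per arm) and from 7.4-8.8 to 5.8-6.9 points (207 per arm).

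**5. Example.** Take 84% against 76% with 165 per arm: SE = √[(0.84×0.16 + 0.76×0.24)/165] = 0.0438. The 90% interval is 8.0 ± 7.2, or 0.8 to 15.2 points. The 95% interval is 8.0 ± 8.6, or -0.6 to 16.6 points. The first supports a superiority claim and the second does not.

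**The case against.** The best defence is that Section 12.3.8.2 was written for the interim's main hypothesis, which is non-inferiority for both effectiveness and safety, and that it states no decision rule for superiority. With a 95% interval mentioned in Section 12.3.8, the text could be read as ambiguous between two levels. One-sided 5% also appears elsewhere in the plan, including for the co-primary safety test. The 95% rule is written for 36 months, the 12-month result triggers no stopping rule, the revision history says the regulator asked for the interim details, and the 95% interval would be on view in any case.

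Some of this stands. The missing decision rule is a real gap, the 12-month result does not touch the 36-month test, and a reader of the report would see both intervals. The rest does not rescue the plan. The wording of 12.3.8.2 covers the comparisons generally, and the 95% interval in 12.3.8 belongs to the descriptive statistics. The safety test at one-sided 5% is a non-inferiority test, so it sets no precedent for superiority. The 36-month effectiveness hypothesis is just as one-sided, yet it gets a 95% interval. Nothing in the document records the regulator's agreement to 90% for superiority. Even on the ambiguous reading, the same edit is needed.

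A further objection is that carrying the 36-month level back to 12 months should reach effectiveness non-inferiority too. That is a fair question for the sponsor, but its answer does not alter the point about superiority.

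**Conclusion.** The concern holds. As written, 12-month superiority is declared at about one-sided 5%, twice the 2.5% that the plan sets for superiority on the same composite at 36 months, and without justification. In practice, observed gains in a band a little over one point wide, from 7.2 to 8.6 points at 80% success and 165 per arm, would be called superior at 12 months although they fail the 36-month rule.

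The error rates are per test and assume equal true success rates. They ignore multiple imputation and any residual confounding from non-random assignment, either of which could shift the realised rates under both intervals. The 12-month success rates and numbers per arm are assumptions, but the doubling follows from the two interval levels and hardly depends on them.

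**What to change.** Add a sentence to Section 12.3.8.2: superiority at 12 months is declared only if the two-sided 95% confidence interval for the propensity-adjusted difference lies entirely above zero, as in Section 12.1.1.3. State there that the 90% interval applies to safety non-inferiority, and name the level for effectiveness non-inferiority, where 90% may stay if the sponsor so chooses.

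This needs no extra subjects or data. The cost is power for the 12-month superiority test (exact, unstratified):

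| True success, mesh vs native | Per arm | 90% interval | 95% interval |
|---|---|---|---|
| 85% vs 70% (planning rates) | 165 | 95.2% | 91.4% |
| 85% vs 70% (planning rates) | 207 | 98.1% | 96.0% |
| 85% vs 75% (assumed) | 165 | 74.1% | 63.5% |
| 85% vs 75% (assumed) | 207 | 82.3% | 73.0% |

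At the planning rates, power stays above the 90% the study was designed for. With a 10-point gain the loss is about 9 to 11 points, which the sponsor should accept knowingly.
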